Study Title: Load Modification Versus Standard Exercise to Inform Treatment for Individuals With Greater Trochanteric Pain Syndrome.

NCT: NCT03571971

Date: January 31, 2022

Approach:

Overview: This pragmatic, feasibility randomized controlled trial (RCT) will consist of up to 64 adult women and men (ratio of approximately 4:1, respectively) between the ages of 18 and 70 who are diagnosed with unilateral greater trochanteric pain syndrome (GTPS) during their initial physician evaluation within the Jameson Crane Sports Medicine Institute physician clinics at The Ohio State University Wexner Medical Center (OSUWMC). All patients will have their standard clinical evaluation with their physician. The group of patients invited to participate in this study will be individuals who meet our clinical diagnostic criteria for GTPS who do not have systemic health or serious musculoskeletal disorders or recent treatment for their hip pain (Table 1). Members of the study team involved in recruitment and consenting will use a two-part process to ensure eligibility using the "Patient Screen Checklist" and the "Eligibility Criteria Checklist," described in detail in the Standard Operating Procedures document. The baseline study visit will occur immediately following the standard clinical examination with the physician.

Table 1. Eligibility Table

Inclusion Criteria	Exclusion Criteria

Ages 18-70, with a unilateral diagnosis of GTPS with:
 
 • Lateral hip pain, worst over greater trochanter, for ≥ 3 months • Pain with palpation over greater trochanter • Average pain intensity of $\geq 4/10$ most days of the week 	
Any of the following treatments within the last 3 months:
 
 • corticosteroid injection in the affected hip • physical therapy or other skilled exercise intervention by a medical or rehabilitation professional

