To inform our sample size estimation for this feasibility randomized controlled trial, we used the available literature which reported a 7% treatment success rate at 4-weeks following a single, standard exercise session (ie. non-load modifying)⁶ and the hypothesized 70% treatment success rate following an 8-week to a supervised load modification program.¹⁸ Conservatively, we estimated that the standard exercise (SE) group and load modification (LM) group would have a 20% and 50% success rate, respectively. **With one-side type I error=0.1, power=80%, and allocation ratio is 1:1, we will need 22 participants in each group (total N=44). We will recruit 64 individuals with GTPS to account for up to 30% attrition over the course of the study due to drop-out.** To fully recruit the study after proper regulatory approval is in place and staff are trained, we anticipate a 15-month recruitment time-frame for the 60 participants. This factors in a recruitment rate of 5 participants per month (see Letters of Support/Collaboration), from an eligible 10 (minimum 50% recruitment rate).

Recruitment and Informed Consent (Figure 1): Prior to enrollment, written informed consent will be obtained from all potential participants after information about the purpose, methods, and demands of the study is provided both verbally and in writing (via the consent documentation) to the participant. The participants for this trial will be recruited from the Jameson Crane Sports Medicine Institute physician clinics at OSUWMC during their on-site medical visit. Once the treating physician confirms GTPS diagnosis through our standardized and validated clinical examination process (Table 1, Inclusion Criteria),^{18,31} the study recruiter will then discuss the study opportunity with the patient and proceed with the consenting process when appropriate.

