B. Randomization, concealed allocation, and blinding: A randomization list will be generated and secured with the study biostatistician prior to the start of the study. It will contain study-specific unique identifiers (ie. GTPS1, GTPS2, etc) and a binary code for treatment group (ie. 0 or 1). A copy of this list will be provided to the Sports Medicine Clinical Research Manager who provides administrative support to all clinical trials in the Sports Medicine Institute. The Manager will determine the group assignment (e.g. 0 = LM, 1 = SE) independent of the biostatistician and the PI. The PI will put together 30 concealed envelopes for each treatment group that contain the group assignment and the appropriate exercise program instructions (SE vs LM) and provide these to the

Manager. The Manager will then label, seal, and place them in a drawer in the physician. The Manager will not be involved in the recruitment, testing, or analysis involved with this trial. She will be the only person with the UID, randomization order, and treatment allocation data all in one place. These data will be stored under lock and key in the private office of the Manager, and in a password-protected file, accessible only to the Manager.

After consent, participants will proceed with testing by a blinded tester. Randomization and group allocation will occur immediately following testing. After testing, the tester will inform the treating physical therapist of group (e.g. 0 vs 1). The drawer with the concealed/sealed envelopes will be accessible to the treating physical therapist and the physicians. The treating physical therapist will select the next available envelope from the appropriate group (0 vs 1) and proceed with the assigned treatment; only when she or he breaks the envelope seal will she or he know the group assignment (LM vs SE).

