Post collection data storage and analysis: A blinded study team member will be responsible for 2D video quality control and creating trial clips for subsequent analysis. Video analysis will begin after the last participant completes their 4-week follow-up. These data will be used to determine measurement variability (intraclass correlation coefficients, standard error of the measurement, and minimal detectable change values) and provide information with regard to changes in movement patterns as a result of program participation. Frontal plane kinematics (peaks and excursions) of the trunk, pelvis, hip, and knee will be calculated (Kinovea version 0.8.15) for each task. Analysis will include the double and single leg static starting postures and peak frontal plane motion (as identified using the joint position tracking function). Lines will be drawn through the long axes of the bones for the shank and thigh, through the ASIS for the pelvis, and from the sternum to the midpoint of the ASIS line (Figure 2). Horizontal and vertical 'lab axes' will be applied to the image to allow calculations relative to pure horizontal (ie. pelvic drop) and pure vertical (ie. trunk lean). Angles will also be calculated with respect to the proximal segment.

Statistical analysis plan:

An intention to treat approach is planned for all analyses, using all participants who were randomized who have available data at 4 week follow-up. Where appropriate, normality will be assessed and non-parametric approaches will be used when assumptions are violated. Demographics and clinical characteristics (ie. age, sex distribution, BMI, baseline pain scores, etc) will be summarized for SE and LM groups, respectively, and compared between the groups using two-sample t-test for continuous outcomes or Fisher's exact test for discrete outcomes.

To evaluate the effect of treatment group allocation on dichotomized treatment success (Aim 1, Hypothesis 1), defined as either: 1) at least 'moderately better' on the Global Rating of Change scale or 2) ≥ 2 point decrease on the Numeric Pain Rating Scale, we will use Fisher's exact test to compare the success rate between SE and LM group. Frontal plane kinematics are a secondary variable of interest (Aim 1, Hypothesis 2). With the available 2D data set, we will compare change scores between groups using independent t-tests and/or effect sizes. These data may serve as preliminary data for future grant applications.

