2. Treatment success is no different between groups (ie. equally effective or ineffective). Compressive forces of the gluteal tendons onto the greater trochanter increase with poor frontal plane control of the hip and pelvis. If is unexpected that modification of these loads through postural and activity modifications and targeted exercises would not be significantly more effective than exercises that disregard this mechanism. However, the lack of effect may indicate the need for more frequent, supervised intervention. If both groups demonstrate equal success, these data would still support our proposed model of a 'physical therapy first' approach.
3. Hip abduction weakness is a clinical feature of GTPS and strength gains may be a critical metric of program success. Hip abduction strength will not be measured, but is associated with poor frontal plane pelvic and hip control during a squatting task. We concede that movement changes may be associated with strength improvements, but contend that improvements in strength do not ubiquitously translate to better movement. Thus, we opted to evaluate movement in this preliminary efficacy and feasibility trial.
4. We may be underpowered to see an effect over the 4 week period. The 4-week follow-up period is consistent with clinical practice and the approach to previous studies^{6,22} evaluating the effect of corticosteroid injections. Further, we modelled our treatment approach on robustly designed RCTs^{14,29,30} in other lower extremity tendinopathy that suggest this 4-week period is enough time to see an effect if one exists.

Benchmarks for success

The first benchmark will be full participant enrollment (N=60) within the first 15 months of the study. The second benchmark will be to maintain 80% 4-week follow-up retention rate; we will assess this at the midpoint of recruitment and testing (N=30) and again at final testing of all participants. Finally, our third benchmark of success will be to have <15% adverse events rates as defined per GROC (see Protection of Human Subjects section)

Citations (in order of appearance)

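### The recruitment target is derived as 64, but the time-frame, envelope supply, enrollment benchmark and midpoint check use 60, which does not cover the stated 30% attrition

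*Combined protocol and SAP*

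**What the plan says.** All statements below are in the combined protocol and SAP.

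- **Overview:** the trial "will consist of up to 64 adult women and men".
- **A. Sample size estimation:** 22 evaluable participants are needed in each group, 44 in total. Then: "We will recruit 64 individuals with GTPS to account for up to 30% attrition over the course of the study due to drop-out". The next sentence reads: "after proper regulatory approval is in place and staff are trained, we anticipate a 15-month recruitment time-frame for the 60 participants". The one after it adds: "This factors in a recruitment rate of 5 participants per month".
- **B. Randomization, concealed allocation, and blinding:** "The PI will put together 30 concealed envelopes for each treatment group", which makes 60. The length of the randomization list is not given.
- **Statistical analysis plan:** the analysis is called intention to treat, "using all participants who were randomized who have available data at 4 week follow-up". For the primary comparison, "we will use Fisher's exact test to compare the success rate between SE and LM group".
- **Benchmarks for success:** the first benchmark is "full participant enrollment (N=60) within the first 15 months of the study". The second is 80% retention at 4 weeks, checked at a midpoint of 30 participants and again at the end.

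**The concern.** One section gives two recruitment totals in consecutive sentences, and the operational parts of the plan follow the total that was not derived. Only 64 is tied to the attrition allowance. If 64 is the target, then the time-frame, the envelopes, the benchmark and the midpoint are wrong. If 60 is the target, the 30% allowance is wrong.

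Feasibility is the trial's purpose and enrollment is its first success criterion. As written, full enrollment can be declared four participants short of the derived target, and a reader cannot tell which total, or which attrition allowance, the trial is held to. Because the analysis keeps only randomized participants with 4-week data, attrition comes straight off the analysed sample.

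**Working it through.** **Inputs.** From the sample size section: success rates of 20% and 50%, one-sided type I error 0.1, power 80%, 1:1 allocation, 22 per group, attrition up to 30%, 5 recruits per month. From the randomization section: 30 envelopes per group. From the benchmarks: full enrollment 60, midpoint 30, retention 80%.

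**1. Reproduce the plan's figures.** Normal approximation for two proportions with pooled variance under the null:

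n = [1.2816·√(2 × 0.35 × 0.65) + 0.8416·√(0.2 × 0.8 + 0.5 × 0.5)]² / 0.30² = 21.9, so 22 per group and 44 in total.

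Attrition: 22/(1 − 0.30) = 31.43, rounded up to 32 per group, so 64. The derivation of 64 is correct.

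**2. Can 60 come from the same inputs?** Dividing the total gives 44/0.7 = 62.9, so 63. The cruder form, 44 × 1.3 = 57.2, gives 58. Neither gives 60.

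**3. What each total delivers against the required 44**

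| Quantity | 60 enrolled | 64 enrolled |
|---|---|---|
| Evaluable at 30% attrition | 60 × 0.7 = 42 | 64 × 0.7 = 44.8 |
| Losses tolerated | 60 − 44 = 16 | 64 − 44 = 20 |
| As a share of those enrolled | 16/60 = 26.7% | 20/64 = 31.25% |
| Evaluable at 80% retention | 60 × 0.8 = 48 | 64 × 0.8 = 51.2 |

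The tolerated losses keep 22 in each group only if they split evenly (8 per group of 30, or 10 per group of 32). At 80% retention, 44/0.8 = 55 enrolled would already be enough.

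**4. Chance of falling short.** If each participant is lost independently with probability 0.3 (an assumption, at the plan's upper limit), the binomial probability of ending with fewer than 44 is about 66% with 60 enrolled and 36% with 64.

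**5. Power at 21 versus 22 per group.** By the formula in step 1, power is 78.7% at 21 and 80.2% at 22. For the planned Fisher's exact test, enumerating both binomials at one-sided 0.1, it is 70.0% at 21 and 69.1% at 22. The reversal comes from the discreteness of the test. The analysis plan does not state sidedness, so the one-sided 0.1 is carried over from the sample size section. On either calculation the change is immaterial. That the exact test has about 70% power where 80% was planned is a separate matter and does not bear on 64 versus 60.

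**6. Envelopes and midpoint.** The 30 + 30 = 60 envelopes fall at least four short of 64. Half of 64 is 32, not 30.

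**7. Recruitment window (secondary).** At 5 per month, 60 takes 60/5 = 12 months and 64 takes 64/5 = 12.8 months. Fifteen months at that rate would give 75. The sample size section starts the clock after approval and training, while the benchmark counts from the start of the study, which could include about three months of start-up.

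**The case against.** The strongest reply is that this hardly matters. The allowance is a ceiling (up to 30%), not an expected loss. If the enrollment and retention benchmarks are both met, 60 enrolled gives 48 evaluable, above 44. A shortfall appears only once attrition passes 26.7%, by which point the 80% retention benchmark has already failed. The gap is four recruits, or two evaluable participants at the worst planned attrition, with no material effect on power. All of this stands, and it limits the weight of the point.

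Several narrower replies also have force:

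- The Overview gives a maximum, which is compatible with enrolling 60. The conflict therefore rests on the sample size section's commitment to recruit 64.
- Nothing is miscalculated: 64 is right on its own inputs. The fault is inconsistency between totals.
- A missed clinic visit need not be a missing outcome. The weekly surveys collect both primary measures, and questionnaires can be completed by link or telephone.
- Both totals fit within 15 months at 5 per month. The window is a wording question, not a demonstrated error.
- The envelope and midpoint differences follow from the same slip; the first is a matter of supply, and the second has no analytic effect.

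None of these removes the conflict. The plan chose to protect against 30% attrition and attached that protection to 64. A total of 60 does not provide it, and no text explains the change.

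**Conclusion.** The concern holds. The plan derives 64 correctly and then works to 60 in its recruitment time-frame, envelope supply, definition of full enrollment and midpoint check. Sixty leaves 42 evaluable at 30% attrition against 44 required, and supports an allowance of 26.7% at most.

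The inconsistency is certain and its numerical effect is small: four recruits, two evaluable participants at the attrition ceiling, and no meaningful change in power. The tolerance figures assume evenly split losses, and the Fisher power figures assume a one-sided 0.1 test. The point should be corrected because it touches both the sample size and a formal success criterion. It does not threaten the trial's validity.

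**What to change.** Adopt one total and use it throughout.

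- **If 64:** prepare at least 32 envelopes per group; change the time-frame and the enrollment benchmark to 64 and the midpoint check to 32; confirm that the randomization list covers 64.
- **If 60:** change the Overview and the sample size section to 60, and restate the attrition allowance as up to about 26% (60 × 0.74 = 44.4, still at least 44; at 27%, 60 × 0.73 = 43.8 is not).

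In either case, state when the 15-month window opens, and make the monthly rate, the window and the total agree.

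The cost is protocol wording and, if 64 is kept, at least four more envelopes. Neither option raises the sample size above what the plan already states.

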All participants will be provided verbal and/or written information (depending on preference) detailing the purpose of the study, type of testing and treatment involved, and potential risks and benefits of participation. Participants will be given time to ask questions and determine their interest in participation without coercion. Patients will be informed during the recruiting process, that if they consent to study participation, they cannot receive a corticosteroid injection that day or during the 4 weeks of the trial. A 4-week follow-up visit to the physician is standard of care for patients with GTPS seen in the Jameson Crane Sports Medicine Institute. This allows physicians to evaluate the effects of common treatments like medication, injections, 'wait and see' advice, and/or physical therapy; at that time, they determine next step interventions based on the initial treatment response. Our research will work within this same 4-week 'trial' period during their regularly scheduled doctor's visits to provide one of two different types of exercise education.

Patients who refuse to forgo injections for 4 weeks will be excluded from the study. Individuals who, for medical reasons, cannot tolerate or should not assume the positions required for the exercises for any reason other than hip discomfort will be excluded. Patients must enroll on the same day as the visit with their physician in order to receive the intervention; however, they do not have to complete the REDCap questionnaires during that visit. All participants will have the option to complete their questionnaires via a unique link to their personal survey or verbally by phone; the online link will be sent to them via email to be completed at their earliest convenience. The participants will be required to sign the IRB-approved consent and HIPAA forms prior to participation in the study.

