To evaluate study retention rates and treatment adherence (Aim 2) we will use descriptive statistics. We will calculate the number of participants in each treatment group who report completing the home program "most (4+) days of the week" and "mostly as directed" on each of the four (4) follow-up REDCap™ surveys. The retention rate and compliance rate will be calculated with 95% confidence interval using exact binomial for each treatment at each follow-up.

H. Feasibility: We will evaluate the feasibility of a future clinical trial to determine the efficacy of load modification exercises and education in improving post-operative function in patients with GTPS by quantifying:

1. The proportion of recruited participants from the total number (a) screened and (b) eligible
2. Participant adherence as measured by: (1) number of weekly surveys completed (ie. number of surveys completed/total number of surveys, (2) weekly home exercise program compliance (self-reported) over the duration of the study, (3) participation retention/attendance at the 4-week follow-up session, and (5) reasons for drop-out and when it occurred (e.g. participant moved out of the area prior to 4-week follow-up)

I. Potential Problems/Alternative Strategies

1. MRI will not be used to confirm gluteal tendinopathy. Grimaldi and colleagues (2017)³¹ performed a diagnostic utility study of 65 individuals with GTPS that showed pain during a 30 second single limb stance was strongly associated with MRI-confirmed gluteal tendinopathy (+LR = 12.2). Importantly, literature also confirms the high prevalence of MRI-confirmed gluteal tendinopathy in asymptomatic individuals,^{31,44,45} highlighting the absence of a strong association between imaging-identified tissue pathology and the clinical syndrome of GTPS. For the aims of this study, this and other validated clinical tests will be used to identify individuals with GTPS. We accept that a small, but insignificant proportion of enrolled participants with clinical indicators of GTPS may not have radiologically-confirmed gluteal tendinopathy. We do not anticipate this will affect the results of this study.

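### The first success benchmark (60 enrolled in 15 months) is 4 short of the plan's target of 64 and, unless its clock includes start-up, corresponds to 4 per month and not the planned 5

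*Combined protocol and SAP*

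**What the plan says.** Section A (Sample size estimation) derives 44 evaluable participants and then sets the enrolment target: "We will recruit 64 individuals with GTPS to account for up to 30% attrition over the course of the study due to drop-out". The Overview agrees, giving 64 as the upper limit.

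The next sentence of section A turns to 60. It says that, "after proper regulatory approval is in place and staff are trained, we anticipate a 15-month recruitment time-frame for the 60 participants". The following sentence explains the window: "This factors in a recruitment rate of 5 participants per month", "from an eligible 10 (minimum 50% recruitment rate").

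The section Benchmarks for success repeats the 60: "The first benchmark will be full participant enrollment (N=60) within the first 15 months of the study". The second benchmark there is 80% retention at 4 weeks. Section B (Randomization) has 30 envelopes prepared for each group, again 60 in total.

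Section H (Feasibility) lists a related measure, "The proportion of recruited participants from the total number (a) screened and (b) eligible", with no threshold. None of the three benchmarks refers to 64, to 5 per month or to 50% uptake.

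**The concern.** Two things do not fit. The plan has two enrolment numbers, 64 and 60, and it calls the smaller one full enrolment. In addition, a window of 15 months for 60 people is presented as following from 5 per month, which it does not.

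In most trials a long recruitment window is harmless planning slack. Here the same pair of numbers is the first criterion by which a feasibility trial will be judged. If it is looser than the plan's own assumptions, recruitment can be reported as successful when enrolment has run below the planned rate and stopped below the number that the sample size section asks for. A future trial planned from that result would inherit the optimistic reading.

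**Working it through.** **Inputs.** From section A: success rates 20% and 50%, one-sided alpha 0.10, power 80%, 1:1 allocation, 22 per group (44 in total), attrition up to 30%, target 64, window 15 months for 60, rate 5 per month, 10 eligible per month, minimum uptake 50%. From Benchmarks for success: 60 in 15 months, retention 80%. From section B: 30 envelopes per group.

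**1. The plan's sample size reproduces.** Normal approximation with pooled variance under the null, no continuity correction:

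- n per group = [1.2816 × √(2 × 0.35 × 0.65) + 0.8416 × √(0.2 × 0.8 + 0.5 × 0.5)]² / 0.30² = 21.9, so 22 per group and 44 in total (power 80.2%).
- Attrition: 44 / (1 − 0.30) = 62.9, so 63; by group, 22 / 0.7 = 31.4, so 32 per group and 64 in total.

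So 64 is the number that the plan's own assumptions lead to.

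**2. The recruitment window does not reproduce.**

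| Quantity | Arithmetic | Result |
|---|---|---|
| Rate implied by 60 in 15 months | 60 / 15 | 4.0 per month |
| Uptake at 10 eligible per month | 60 / 150 | 40% |
| Time to 60 at 5 per month | 60 / 5 | 12 months |
| Time to 64 at 5 per month | 64 / 5 | 12.8 months |
| Number enrolled in 15 months at 5 per month | 5 × 15 | 75 |
| Rate needed for 64 in 15 months | 64 / 15 | 4.27 per month |
| Uptake for 64 in 15 months | 64 / 150 | 42.7% |

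**3. The clock.** Section A starts its 15 months once approvals and training are complete, so start-up cannot explain the gap there. The benchmark counts from the start of the study. If 3 of those months were start-up, 60 / 12 = 5.0 per month and 60 / 120 = 50%, which matches the plan. With 2 months of start-up it is 60 / 13 = 4.6 per month, and with 1 month 60 / 14 = 4.3.

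**4. Effect on evaluable numbers.**

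| Enrolled | At 30% attrition | At 80% retention |
|---|---|---|
| 60 | 42.0 | 48.0 |
| 64 | 44.8 | 51.2 |

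With 60 enrolled, the evaluable number falls below 44 only if retention is under 44 / 60 = 73.3%.

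**5. How hard the benchmark is to meet.** Assume Poisson accrual at a true 5 per month, so a mean of 75 in 15 months. The chance of enrolling fewer than 60 is 3.3%; of fewer than 64, 8.9%. With 64 in 13 months (mean 65), the chance of missing is 43%.

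**The case against.** The strongest reply is that a plan can allow for 5 per month and still set a longer window. Slack is ordinary prudence, and a pass mark set at the expected count would fail many trials that recruit exactly as planned: 64 in 13 months would be missed about 43% of the time. This stands as an argument for keeping 15 months. It does not settle the point, because no slack is stated and section A presents the window as built on 5 per month.

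A second reply is that the benchmark's clock may include start-up. That also stands: with about 3 months of start-up the rate is exactly 5 per month. The documents do not say so, and section A's clock is defined differently, so the start has to be stated.

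Three stronger readings might be inferred and are not supported:

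- **That meeting the benchmarks would leave the trial too small.** A trial that meets both the enrolment and the retention benchmark has 48 evaluable, above 44. The figure of 42 needs 30% attrition, which would fail the retention benchmark.
- **That recruitment would be declared feasible at 40% uptake.** The 40% holds only with 10 eligible each month. The benchmark has no uptake criterion, so fewer eligible patients would mean higher uptake at the same enrolment. Section H reports recruited over eligible separately, so low uptake would be visible.
- **That uptake will be inflated by removing patients who decline to go without an injection.** Recruitment and Informed Consent says "Patients who refuse to forgo injections for 4 weeks will be excluded from the study", and Table 1 does not list this. But section H does not define who counts as eligible, the eligibility checklists are in a Standard Operating Procedures document that is not part of the text, and nothing gives the number of such patients. The first benchmark counts enrolment and is unaffected either way.

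**Conclusion.** The inconsistency is real and should be corrected. The plan's assumptions lead to 64, while the time-frame, the envelopes and the first benchmark use 60, so the benchmark can in any case be met 4 short of the target. On section A's clock, 60 in 15 months is 4 per month against a stated 5, and 40% uptake against a stated minimum of 50% if 10 patients are eligible each month. For the benchmark itself, the shortfall in rate depends on its clock not including about 3 months of start-up, and the shortfall in uptake depends on the eligible flow as well.

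The consequence is confined to how feasibility is read. The primary comparison of success rates is not affected, and the evaluable number falls short of 44 only if retention is below 73.3%. Whether the gap is deliberate slack or a figure left unaligned cannot be told from the documents.

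**What to change.** - Use 64 wherever the enrolment number appears: the time-frame in section A, the first benchmark, and 32 envelopes per group in section B.
- State when the 15 months begin, and use the same start in section A and in the benchmark.
- Keep 15 months. State the minimum that the benchmark then implies, 64 / 15 = 4.3 per month (43% of 10 eligible), and label 5 per month (50%) as the expected rate and not the minimum. These figures take the clock as starting when recruitment opens; if it starts earlier, recompute them for the shorter recruiting period.
- Report the proportion recruited of those eligible with an exact 95% confidence interval against the stated minimum, as the plan already does for retention and compliance.

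**Cost.** These are changes of text, plus four more envelopes. The benchmark becomes slightly harder to meet: at a true 5 per month, with Poisson accrual assumed, the chance of missing it rises from about 3% to about 9%. The stated minimum rate and uptake will also look less favourable than the present 5 per month and 50%.
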